### 5.1.3 Outcome Measures

Primary and exploratory endpoints will be based on the outcome measures as described in Table 2.

Table 2. Outcome Measures

Endpoint	Outcome Measure
Compliance	
 
• Compare rate of compliance (# of days used/total study days) to prescribed treatment between FT-CC PASSIVE and FT-CC ACTIVE Subjects at 30 and 60 days
 

Change in Arm Girth	
 
• Comparison between baseline and day 30/60 arm girth measurement
 

Quality of Life	
 
• Comparison between baseline, 30 day, and 60 day surveys
 

Symptom Assessment	
 
• Comparison between baseline, 30 day, and 60 day surveys
 

## 5.2 Subject Selection

The target population includes patients who have unilateral BCRL. Only patients who meet the criteria below will be considered for the study. A total sample of 30 subjects will be randomized.

### 5.2.1 Inclusion Criteria

1. Female 18 years of age or older
2. Diagnosis of unilateral breast cancer-related lymphedema
3. Willing and able to give informed consent (remotely or in person)
4. Willing and able to comply with the study protocol requirements and all study-related visit requirements, including the ability to participate remotely
5. Willing and able to receive text messages from sponsor

### 5.2.2 Exclusion Criteria

1. In-home use of PCD within previous 3 months

2. Phase-one CDT within previous 1 month or planned phase-one CDT during study participation  
*Phase-one CDT defined as professionally administered MLD and/or multi-layer short stretch compressive bandaging.*
3. Inability to be fit for PCD garments
4. Heart failure (acute pulmonary edema, decompensated acute heart failure)
5. Acute venous disease (acute thrombophlebitis, acute deep venous thrombosis, acute pulmonary embolism)
6. Active skin or limb infection/inflammatory disease (acute cellulitis, other uncontrolled skin or untreated inflammatory skin disease) on the arms or trunk
7. Currently receiving treatment for cancer with curative intent.
8. Any circumstance where increased lymphatic or venous return is undesirable
9. Currently pregnant or trying to become pregnant
10. Known inability to receive cell phone connection where FT-CC therapy will be administered

#### **5.3 Point of Enrollment and Randomization**

Subjects will be considered enrolled in the study once the Informed Consent Form (ICF) is signed and all inclusion/exclusion criteria are met. The investigator will keep a record, the subject screening log, of subjects who enter screening. Any subjects who do not meet inclusion/exclusion criteria will be considered screen failures.

Randomization codes will be generated by a statistician in a permuted block design. The block size will be balanced within each block and will maintain a 1:1 ratio between the treatment groups. The randomization assignment will be obtained from the electronic data capture (EDC) database and assigned sequentially as soon as a subject is considered enrolled.

If a subject does not meet all the eligibility criteria or meets any of the exclusion criteria but is randomized in error, or incorrectly started treatment, the Investigator should inform Tactile Medical immediately.

#### **5.4 Subject Discontinuation or Withdrawal**

Subject participation may be discontinued prior to study completion for any of the following reasons:

- **Withdrawal of Consent**  
Subjects may withdraw their consent to participate at any time. If a subject withdraws consent, previous information that has already been obtained will be available for analysis.
- **Discretion of the Principal Investigator**

Subjects may be withdrawn at the investigator's discretion in the event of changes in the subject's health, or other reasons based on the investigator's clinical judgment.

When a subject withdraws prior to completing the study, the reason for withdrawal will be recorded.

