### **6.0 Study Assessments**

In an effort to reduce potential exposure to COVID-19, all study assessments are intended to be performed in a contactless manner (i.e., telephone, video conference, etc). If an assessment is done in-person, the reason will be documented, (e.g., required for adverse event assessment, requested by subject, risk for COVID-19 eliminated, assessment performed in conjunction with another clinic visit, etc.).

CRFs and Data Clarification Forms (DCFs) will be used for data collection and query handling. The Investigator will ensure the accuracy, completeness, and timeliness of the data recorded and responses to data queries according to the Clinical Trial Agreement (CTA).

All data entry, storage, transmission, and management will be conducted using iMedNet, a 21 code of federal regulations (CFR) Part 11 compliant EDC system. When all data have been validated, signed, and locked, the database will be locked and available for analysis.

All devices and testing procedures outlined are standard of care or approved/cleared for use by the Food and Drug Administration (FDA) with the exception of FT-CC. Tactile Medical will provide qualified trainers to train the subject on how to use the FT-CC.

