#### 6.4 **Day 60 ( $\pm 7$ days) Follow-Up Visit**

The subject will be contacted for the following assessments:

- Weight (only required if they have access to a scale and can self-report)

- Medication Review
- Lymphedema Treatment Review
- Arm Girth
- LYMQOL ARM
- SF-36
- LSIDS-A
- AE & Device Observation Assessment

After the subject has completed their Day 60 follow-up visit, they will be exited from the study and the FT-CC device will be collected. Return of the FT-CC may be done by the subject returning the controller to the clinic or by shipping it back from their home in a box provided by Tactile Medical.

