## 7.9 Randomization

If the subject meets all of the inclusion criteria and none of the exclusion criteria, they will be randomly assigned to ACTIVE FT-CC or PASSIVE FT-CC.

Randomization will occur via entering the randomization CRF in the EDC system. The randomization assignment should not be shared with the research subject.

The randomization assignment cannot be changed or chosen by the subject or the investigator.

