## 16.0 Statistical Methods

### 16.1 Sample Size Determination

No power calculations were used to derive a sample size for this study given this study seeks to identify which health outcomes should be used for a larger randomized controlled trial in the future. The desired target sample size for this feasibility study is 10 analyzable data sets for each group. It is estimated that up to 30 subjects will need to be enrolled to achieve 60 day follow-up data on 20 subjects.

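### Withdrawal by the investigator for a change in health ends study participation, with no provision to keep following a woman who has not withdrawn consent, so the health-outcome summaries may look too favourable

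*Combined protocol and SAP*

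**What the plan says.** Section 5.4 opens with "Subject participation may be discontinued prior to study completion for any of the following reasons" and gives two reasons: withdrawn consent and the discretion of the principal investigator. Under the second it says "Subjects may be withdrawn at the investigator's discretion in the event of changes in the subject's health", and it also admits other grounds that rest on the investigator's clinical view.

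On data, Section 5.4 says two things. After withdrawn consent, "previous information that has already been obtained will be available for analysis". For any withdrawal, "When a subject withdraws prior to completing the study, the reason for withdrawal will be recorded". It describes no early-termination visit, no later contact, and no status in which device use has ended but follow-up goes on. No other section supplies these.

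Section 6.0 states that "all study assessments are intended to be performed in a contactless manner". The Day 60 visit in Section 6.4 is a contact: "The subject will be contacted for the following assessments". Girth is taken with a tape measure supplied to the subject (Section 7.8). LYMQOL ARM and LSIDS-A are completed online or by mail (Sections 7.10.1 and 7.11). No mode is given for the SF-36, so only the general statement in Section 6.0 covers it.

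Section 16.2 bases summaries on reported data, plans no imputation, and plans no explicit reporting of missing data in the tables. Section 16.1 enrols up to 30 women to "achieve 60 day follow-up data on 20 subjects".

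**The concern.** A woman can be removed for a change in health without withdrawing consent. As written, her later girth, quality of life and symptom values are then not collected, although none of these measurements needs the device in hand.

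The loss may be informative. Section 9.0 names increased swelling and pain or discomfort as likely reactions, with cellulitis and new trunk edema less likely. Girth and the LSIDS-A measure swelling and symptoms directly. If some removals follow such events, the women who remain are a more favourable group, and an available-data summary carries that forward with no adjustment and no planned count of the missing.

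These endpoints are exploratory, but they matter here. The effect of compliance on them is part of the objective in Section 4.0, and Section 16.1 says the study is meant to show which health outcomes to carry into a larger trial. Section 16.2 puts the emphasis on estimation, so a biased estimate touches the study's main product even though no test is planned.

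**Working it through.** **The plan's own figure.** Section 16.1 gives 30 enrolled for 20 with 60-day data but no loss rate. The implied loss is (30 − 20)/30 = 1/3, and 20/(1 − 1/3) = 30, so the figure is consistent with itself. With 1:1 allocation (Section 5.3), 30 women make 15 per arm. Against a target of 10 analysable sets per arm, that leaves 15 − 10 = 5 losses per arm.

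**Shift in the pooled Day 60 mean.** Inputs:
- Women with Day 60 data: 20 (Section 16.1).
- Women removed by the investigator: k = 3 or 5. This is assumed. It lies within the allowance of 10 losses, but the documents do not say how many of those would be investigator removals.
- Gap between removed and retained women: g = 0.5 or 1.0 SD, in the unfavourable direction. This is assumed.

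If the retained mean is m, the mean of all 20 + k women is m − g × k/(20 + k). The available-data mean is therefore too favourable by g × k/(20 + k):

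| k | k/(20 + k) | g = 0.5 SD | g = 1.0 SD |
|---|---|---|---|
| 3 | 3/23 = 0.130 | 0.07 SD | 0.13 SD |
| 5 | 5/25 = 0.200 | 0.10 SD | 0.20 SD |

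**Scale.** With 10 women in each of two groups, the 95% half-width for a difference in means is t(0.975; 18) × √(2/10) = 2.101 × 0.447 = 0.94 SD. The assumed shift is small beside that. It is, however, systematic, and an interval computed from the retained women does not reflect it.

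**How retained women would be classed.** Section 5.1.2 analyses these endpoints by compliance category: an average of 1–4 or 5–7 days of use per week. Assume the average is taken over 60 days. A woman who uses the device daily for 30 days and is then taken off it averages 7 × 30/60 = 3.5 days per week and counts as partially compliant. One taken off after 8 days averages 7 × 8/60 = 0.93 and fits neither category. Continued follow-up alone could therefore place poor outcomes in the low-use group when ill health caused the low use.

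**The case against.** The strongest case against is that Section 5.4 is permissive. Nothing says a woman who stops using the device must be withdrawn. Non-use is what the primary endpoint measures, and Section 5.5 lets the investigator change settings without withdrawal. A site could stop the device and keep her in follow-up today. That stands, and it makes this a missing provision rather than a rule that forces data loss. It does not remove the gap, because once the investigator does withdraw a woman, nothing provides for further data.

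Several stronger readings are tempting, and the documents do not support them:
- *The women removed are those whose lymphedema worsens.* Section 5.4 speaks of changes in health and of other grounds. A link to the arm is plausible from Section 9.0, but that section also describes the therapy as minimal risk.
- *Removals eat into the target of 10 per arm.* They draw first on the allowance of about 5 per arm.
- *The ACTIVE versus PASSIVE contrast in health outcomes is biased.* That contrast is not planned. Section 5.1.2 uses compliance categories, and Section 5.1.3 plans an arm comparison for compliance only.
- *Knowledge of the arm drives removals.* Section 7.9 says only that "The randomization assignment should not be shared with the research subject", so the investigator may know it. But both arms have the same device and prescription, and only the reminders differ. The documents give no reason why this would affect health-based withdrawal.
- *Every remaining assessment can be remote.* Section 6.0 itself names adverse event assessment as a reason for an in-person visit.

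**Conclusion.** The point holds as a gap in the follow-up provisions. Investigator withdrawal for a change in health ends participation, no follow-up is provided for a woman who still consents, and the available-data summaries may therefore be too favourable.

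On the stated assumptions the pooled shift is 0.07 to 0.20 SD. It rests on two quantities the documents do not give: how many women are removed this way, and how their outcomes differ from the rest. If the health changes are unrelated to the arm, the shift could be near zero. The primary compliance endpoint is not the subject of this point, and with no tests planned there is no error-rate consequence. The change is worth making because it is cheap and protects estimates meant to guide a later trial, not because a large bias has been shown.

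**What to change.** - **Section 5.4:** separate the end of device use from the end of study participation. State that a woman whose device use ends, or who would otherwise be withdrawn by the investigator, still gives the scheduled Day 30 and Day 60 assessments (girth, LYMQOL ARM, SF-36, LSIDS-A and adverse events), remotely where possible. The exceptions are that she withdraws consent, or that the investigator documents that further contact is not appropriate. Record the date and reason for each kind of stop.
- **Section 16.2:** keep her in her randomized arm for any by-arm summary. For the compliance-category summaries of Section 5.1.2, flag women whose device use the investigator ended and show results with and without them, so that low use caused by ill health is not read as an effect of low compliance.

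The decision about device use stays with the investigator. The cost is a protocol and consent sentence, at most two already scheduled contacts for a few women, and one extra summary.

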#### **5.5 Randomization Assignment and Treatment Duration**

Eligible patients will be randomized (1:1) to one of the following groups for 60 days:

- ACTIVE FT-CC – Text message reminders will be sent if subject does not use device for 2 consecutive days
- PASSIVE FT-CC – Text message reminders will not be sent to subjects

The FT-CC prescription will be a daily 60-minute U1 unilateral treatment at normal pressure. Settings and programs may be modified by the discretion of the investigator, if needed, and these modifications will be documented. If subjects are assigned to the ACTIVE FT-CC group and their device is not used for 2 consecutive days, they will receive a text message reminding them to use their device. If subjects are assigned to the PASSIVE FT-CC group, they will not receive text message reminders.

If subjects assigned to the ACTIVE FT-CC group are not able to receive text messages due to cellular connectivity or text transmission issues, alternate methods may be used to remind the subject to use their device and will be documented on the Case Report Form (CRF).

#### **5.6 Study Timeline**

The expected study duration is approximately 10 months with 2-3 months spent on activation, 5 months enrolling and following subjects, and 2 months completing the data analysis.

### **6.0 Study Assessments**

In an effort to reduce potential exposure to COVID-19, all study assessments are intended to be performed in a contactless manner (i.e., telephone, video conference, etc). If an assessment is done in-person, the reason will be documented, (e.g., required for adverse event assessment, requested by subject, risk for COVID-19 eliminated, assessment performed in conjunction with another clinic visit, etc.).

CRFs and Data Clarification Forms (DCFs) will be used for data collection and query handling. The Investigator will ensure the accuracy, completeness, and timeliness of the data recorded and responses to data queries according to the Clinical Trial Agreement (CTA).

All data entry, storage, transmission, and management will be conducted using iMedNet, a 21 code of federal regulations (CFR) Part 11 compliant EDC system. When all data have been validated, signed, and locked, the database will be locked and available for analysis.

All devices and testing procedures outlined are standard of care or approved/cleared for use by the Food and Drug Administration (FDA) with the exception of FT-CC. Tactile Medical will provide qualified trainers to train the subject on how to use the FT-CC.

#### 6.1 **Screening/Baseline Visit**

If a patient appears eligible to participate based on medical history, they will be contacted or approached to assess interest. If the subject is interested in learning more, an ICF will be provided to them (in-person, electronically, or via mail) and the subject will be given adequate time to review and ask questions. If the subject decides to participate and provides documented informed consent, they will undergo the following assessments:

- Obtain medical history
- Administer a serum or urine pregnancy test for all female subjects of child-bearing potential (if this is required, it will be done at the clinic)
- Height and weight
- Medication Review
- Lymphedema evaluation
- Lymphedema treatment review
- Arm Girth
- Randomization
- LYMQOL ARM
- SF-36
- LSIDS-A
- FT-CC Garment Measurements

#### 6.2 **Day 0 – Training**

FT-CC training should occur within 21 days of the Screening/Baseline visit. The training may occur remotely using electronic means (i.e., telephone, video conference, etc), or in-person. Training will be performed by qualified Tactile Medical personnel.

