## 6.5 Study Schedule of Activities

The study schedule of activities is shown below (Table 3).

Table 3. Schedule of Study Activities

Assessments	Screening/Baseline	Day 0 - Training	Day 30	Day 60
Visit Window	N/A	Within 21 days after Screening/Baseline	±7 Days	±7 Days
Informed Consent	X			
Demographics & Medical History	X			
Pregnancy Test (if applicable) 	X			
Inclusion/Exclusion Assessment	X			
Height and Weight	X 		X 	X 
Medication Review	X		X	X
Lymphedema Evaluation	X			
Lymphedema Treatment Review	X		X	X
Arm Girth	X		X	X
Randomization	X			
Quality of Life Assessments (LYMQOL ARM, SF-36)	X		X	X
Symptom Assessment (LSIDS-A)	X		X	X
FT-CC Garment Measurements	X			
FT-CC Training		X		
AE & Device Observation Assessment			X	X

If pregnancy test is required, it will be performed in the clinic

Height collected at Screening/Baseline visit only; height and weight collected via self-report for subjects with access to scale or from subject's most recent medical history

Weight collected via self-report if subject has access to a scale at home

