### 7.6 Lymphedema Evaluation

Research personnel will confirm a diagnosis of unilateral breast cancer-related lymphedema by review of the subject's medical records.

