#### 7.13 **FT-CC Training**

After all baseline assessments have been performed, the subject will be contacted by a Tactile Medical trainer to schedule a training visit on how to use the FT-CC. This training may occur virtually, at the clinic, or in the subject's home. Training may be conducted up to 21 days after the baseline visit.

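### Girth, quality of life and symptoms are measured 0 to 21 days before FT-CC training and not repeated before first use, so change from baseline can include a period without the device of unequal length

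*Combined protocol and SAP*

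**What the plan says.** Section 6.1 lists arm girth, LYMQOL ARM, SF-36 and LSIDS-A at the Screening/Baseline visit. Table 3 in Section 6.5 schedules them again at Day 30 and Day 60. The questionnaire rows read "Quality of Life Assessments (LYMQOL ARM, SF-36) X X X" and "Symptom Assessment (LSIDS-A) X X X", with the three crosses under Screening/Baseline, Day 30 and Day 60. The arm girth row has the same pattern. The only activity marked for Day 0 is training.

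On the interval, Section 6.2 says "FT-CC training should occur within 21 days of the Screening/Baseline visit" and Section 7.13 repeats it: "Training may be conducted up to 21 days after the baseline visit". Section 7.13 also fixes the order: "After all baseline assessments have been performed, the subject will be contacted by a Tactile Medical trainer to schedule a training visit".

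The girth outcome in Table 2 (Section 5.1.3) is "Comparison between baseline and day 30/60 arm girth measurement"; the quality-of-life and symptom outcomes likewise compare baseline with the 30- and 60-day surveys. Section 5.1.2 analyzes these exploratory endpoints by observed compliance category. Section 16.2 plans descriptive summaries only. No section repeats the four measures at Day 0, limits the age of the baseline value, or reports or adjusts for the lag.

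**The concern.** The exploratory aim is to relate device use to change in girth, quality of life and symptoms. The value used as the starting point may be up to three weeks old when the woman first has the device in use, and the age of that value differs between women. Any change in the limb or the scores during the gap is counted in the change attributed to the on-device period.

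A gap is also the usual case. The trainer makes contact only after the baseline assessments, garments are sized from measurements taken at that visit (Section 7.12), and device and garments are then shipped to the subject (Section 8.0).

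Randomization balances the lag between ACTIVE and PASSIVE in expectation. It does nothing for compliance categories, which are formed after randomization. Section 16.1 says the study is meant to identify which health outcomes a larger trial should use, and these are the outcomes affected. With 20 analyzable subjects targeted and no tests planned, the descriptive estimates are the product of the study.

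**Working it through.** The plan gives no figure of its own for this point, so there is nothing to reproduce. The check is day arithmetic.

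**Inputs**
- Lag L from baseline to training: 0 to 21 days (Sections 6.2 and 7.13).
- Visit day V: 30 ± 7 and 60 ± 7 (Sections 6.3 and 6.4), counted from training. This counting is inferred from the Day 0 label.
- Mid-range lag of 10.5 days: assumed, half of 21.

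**Share of the change interval before training** = L / (L + V)

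| Lag | Nominal Day 30 | Nominal Day 60 |
|---|---|---|
| 0 days | 0/30 = 0% | 0/60 = 0% |
| 10.5 days (assumed) | 10.5/40.5 = 26% | 10.5/70.5 = 15% |
| 21 days | 21/51 = 41% | 21/81 = 26% |

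Across the visit windows at a 21-day lag, the Day 30 share runs from 21/58 = 36% to 21/44 = 48%, and the Day 60 share from 21/88 = 24% to 21/74 = 28%.

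**Length of the change interval**
- Now, Day 30: 0 + 23 = 23 to 21 + 37 = 58 days.
- Now, Day 60: 0 + 53 = 53 to 21 + 67 = 88 days.
- With baseline at Day 0: 23 to 37 and 53 to 67 days. The spread falls from 35 to 14 days, which is the visit window alone.
- With baseline up to 3 days before Day 0 (assumed), at most 3/33 = 9% and 3/63 = 5% of the nominal intervals fall before training.

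**If Day 30 and Day 60 were counted from baseline instead**, time since training would be 30 − 7 − 21 = 2 to 37 days at Day 30 and 60 − 7 − 21 = 32 to 67 days at Day 60. The unevenness would remain, and the shortest exposure would be very short.

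**Possible size, on assumptions only.** The documents give neither a drift rate nor an SD.
- If an outcome drifted 0.1 to 0.5 SD per 30 days without the device, a 21-day lag would add 0.1 × 21/30 = 0.07 to 0.5 × 21/30 = 0.35 SD to that woman's change.
- If girth drifted 0.1 to 0.3 cm over 21 days, and mean lag were 14 days in low users and 7 in high users, the spurious difference between categories would be (14 − 7)/21 × 0.1 to 0.3 cm = 0.03 to 0.10 cm.

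**Care during the gap.** Section 7.7 asks about garments and other prescribed treatment in the last 7 days, at baseline and at Days 30 and 60. The earliest Day 30 visit is Day 23, so its recall reaches back to Day 16. None of the three recall periods covers the gap.

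**The case against.** The strongest reply is that the shares above are shares of calendar time, not of effect. They matter only if the outcomes move during the gap, and the documents do not show that they do. Eligibility limits the scope for movement: in-home PCD use in the previous 3 months is excluded, as is "Phase-one CDT within previous 1 month or planned phase-one CDT during study participation". Twenty-one days is a maximum, and the girth illustration comes to 0.3 to 1.0 mm on a tape reading made at home. The affected comparisons are exploratory, descriptive and non-randomized whatever the lag. Moving the measures while leaving randomization in place would also put baseline after assignment, when site staff can know the arm. All of this stands as a limit on importance. None of it removes the unequal interval.

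Several stronger readings are tempting and are not supported:
- **That the baseline is not a pre-treatment value.** It is taken before the device is in use; it is simply not the latest such value.
- **That the gap is untreated.** It is a period without FT-CC. Compression garments and other prescribed care may continue.
- **That every change score is affected.** A woman trained on the day of baseline would have no lag.
- **That slow schedulers use the device less.** No section links lag to use, and part of the lag may be trainer scheduling and shipping.
- **That limbs are still changing after phase-one CDT.** The one-month exclusion addresses this in part, and the documents give no data on it.

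**Conclusion.** The timing is as described, and no other section resolves it. Where the lag is not zero, change from baseline in girth, LYMQOL ARM, SF-36 and LSIDS-A spans a period without FT-CC of unequal length: up to 41% of the nominal Day 30 interval and 26% of the Day 60 interval, and 26% and 15% at an assumed 10.5-day lag. This adds avoidable variation in follow-up length. It could bias the comparison by compliance category if lag differs between categories, which is possible but not shown. The size of any effect on the outcomes is unknown.

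The figures assume that visit days count from training and that first use follows training promptly. The 21 days is worded as a target for training, and no date of first use is defined, so the real gap could be longer.

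A reader might infer that the primary result is compromised too. It is a rate of days used, not a change from baseline, so this point does not reach it. This is a cheap improvement to the exploratory part of the study, not a fault in its main comparison.

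**What to change.** In Table 3 and Sections 6.1 and 6.2, collect arm girth, LYMQOL ARM, SF-36 and LSIDS-A at Day 0 or in the few days before it, and before the first FT-CC session. Define these values as baseline in Table 2. Leave eligibility checks and garment measurements at Screening. None of the four measures is needed earlier: Section 7.6 has staff "confirm a diagnosis of unilateral breast cancer-related lymphedema by review of" the subject's medical records, and garment sizing uses separate measurements.

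Handle randomization in one of two ways:
- Enter it after the four measures. Both arms receive the same device, so shipping need not wait for the assignment. Section 5.3, which assigns the arm as soon as a subject is enrolled, would need the matching change.
- Keep it at Screening, relying on Section 7.9, under which the subject is not told her arm.

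Also report the lag from Screening to Day 0 by compliance category. The transmitted usage data described in Section 3.2 could supply the date of first use as well.

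No assessment is added. Girth is read at home with a supplied tape (Section 7.8), and LYMQOL ARM and LSIDS-A can be completed online (Sections 7.10.1 and 7.11). The costs are a schedule and EDC amendment, coordination with the sponsor's trainer, earlier dispatch of questionnaires to women who complete them by mail, and no outcome baseline for women lost before Day 0. Those women have no on-device outcome to compare, but their baseline values would no longer be there to describe who was lost.
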